ESO-SPARE: Esophagus-sparing radiotherapy for cervical and thoracic spinal cord compression. A randomized phase 3 trial.

Statistical Analysis Plan

Trial registration number:

Danish Ethical committee: H-20069184

Clinicaltrials.gov: NCT05109819

Principal investigator:

[name], PhD

Department of Oncology, Herlev and Gentofte University Hospital

[name]

[name]

[contact]

E-mail: [contact]

Sponsor:

Associate professor [name] PhD

Herlev and Gentofte Hospital Copenhagen University, Department of Oncology

[name]

[name]

[contact]

E-mail: [contact]

Participating centers

Dept. of Oncology, Copenhagen University Hospital – Herlev and Gentofte

[name]

Local investigator: [name]

Dept. Of Oncology, Copenhagen University Hospital – Rigshospitalet

[name]

Local investigator: [name] MD PhD

Principal investigator:.....	1
Sponsor:.....	1
Study Description	3
Summary.....	3
Condition or disease.....	3
Intervention.....	3
Purposes	3
Primary endpoints	4
Secondary endpoints.....	4
Trial design.....	4
Sample size	6
Recruitment, withdrawal, and follow-up	8
Statistical principles.....	8
Analysis.....	8
Reporting of the radiation details	12
Double included patients	12
Missing data.....	13
Statistical software	13
Analysis summary.....	14
References.....	16

Study Description

Summary

This study is a randomized, single blind, phase III clinical trial investigating if esophagus-sparing radiotherapy can reduce dysphagia in patients with cervical and thoracic Metastatic Spinal Cord Compression (MSCC), without hampering the patient's ambulatory function.

Co-primary endpoints are severity of patient reported dysphagia within five weeks after treatment start measured by PRO-CTC-AE and ability to walk at nine weeks measured by the mobility dimension in EQ-5D-5L.

Condition or disease

MSCC in the cervical and thoracic spine from any cancer type, treated with palliative radiotherapy of 1-10 fractions.

Intervention

Esophagus-sparing radiotherapy.

Purposes

1. To investigate if esophagus-sparing radiotherapy can decrease patient reported dysphagia without compromising the patient's ambulatory function.

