We assume that we can decrease maximum esophageal dose from 30 Gy to 10 Gy and that this will result in a 50% decrease in risk of early esophageal toxicity. We want to conduct a phase III trial with 1:1 randomization between standard VMAT and experimental esophageal VMAT. Prior data (2) indicate that the rate of early esophageal toxicity with standard VMAT is 0.6. If the true early esophageal toxicity rate in the esophagus sparing VMAT arm is 0.3, conventional power calculation indicates that we would need to include 62 patients in each arm, to be able to reject the null hypothesis that the toxicity rates for experimental and control arms are equal with a probability (power) of 0.9. The Type I error probability associated with the test of this null hypothesis is 0.05 and calculations are performed assuming Fisher's exact test. However, with this patient population we anticipate high rate of heterogeneity, and we need to account for loss of follow-up due to patients dying early or being too frail. We increase the study size to 100 patients in each arm to account for these challenges. Patients will be stratified according to fractionation scheme and treating center.

Ambulatory function as a co-primary endpoint

We wish to demonstrate that the improvement in esophageal toxicity does not come at a price of reduced effect of the radiation. As a prioritized secondary endpoint, we choose ambulatory function (preserved ability to walk) measured on a 4-point scale. We assume that the conventional arm follows the distribution of the SCORAD trial and test our ability to detect a difference from an assumed inferior experimental arm in terms of ambulatory function, see Table 2.

If the underlying “true” distribution on ambulatory grades is as depicted in the table and we assume 66 patients per arm are evaluable, we find that 84% of simulated trials would lead to statistically significant differences detected with a Wilcoxon rank sum test for comparing the trial arms. In other words, the power of the trial is enough to detect a deterioration according to the able, which would lead to rejection of the experimental treatment.

The power of ESO-SPARE is enough to detect a difference in ambulatory function as seen in Table 2

	Conventional arm	Experimental arm
Grade 1: Ambulatory without the use of walking aids	22	11
Grade 2: Ambulatory with walking aids	44	32
Grade 3: Unable to walk	26	37
Grade 4: Absence or flicker of motor power in any muscle group	8	20

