Table 2: Distribution of ambulatory function. The conventional arm follows the SCORAD trial (Hoskin et al., 2019).

Recruitment, withdrawal, and follow-up

Enrollment, intervention, allocation, follow-up, and data analysis will be summarized in a CONSORT diagram in accordance with CONSORT 2010 guidelines (4)

Statistical principles

Confidence intervals and P values

Level of significance: $p < 0.05$ with no adjustment for multiplicity. Confidence intervals are reported at 95 % limits (bound by zero) and calculated by the binominal distribution for rates and as per Kaplan-Meier method for time-to-event analyses.

Analysis

We will report our data in accordance with the CONSORT 2010 guidelines including the CONSORT Patient-Reported Outcome (PRO) extension (4,5) .

Analyses will be performed per-protocol for all patients who have received any study treatment.

Primary analysis of NCI-PRO-CTC-AE toxicity will only include weeks where ≥ 3 days questionnaires are completed.

Primary analysis of EQ-5D-5L and EORTC-QLQ-C30 will only include completed questionnaires.

All CTC-AE and PRO-CTC-AE grades will be reported.

Missing data will be described in detail, see missing data section.

A. Co-primary endpoints

1. Peak dysphagia (difficulty swallowing) measured by NCI-PRO-CTC-AE within 5 weeks after start of radiotherapy (daily measurements).

PRO-CTC-AE responses are scored from 0 to 4, with 0 representing "None" and 4 representing "Very severe". For each patient the peak value within 5 weeks after start of radiotherapy (daily measurements) will be included in the analysis. Difference in scores between treatment arms will be compared using Wilcoxon rank-sum test.

2. Ambulatory function measured by EQ-5D-5L mobility dimension at 9 weeks after start of radiotherapy.

EQ-5D-5L measures individual generic health status using 5 dimensions: mobility, self-care, usual activities, pain/discomfort, and anxiety/depression. Each dimension has 5 levels depending on the severity of symptoms, with 1 representing “No problems” and 5 representing “Extreme problems”. Difference in scores between mobility dimension treatment arms will be compared using Wilcoxon rank-sum test.

B. Severity of dysphagia, nausea and dyspepsia measured by NCI-PRO-CTC-AE [Time Frame: Week 1-9 after start of radiotherapy (repeated measurement)].

CTC-AE responses are scored from 0 to 4, with 0 representing “None” and 4 representing “Very severe”.

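### Preserved walking is a stated aim, but its only planned between-arm analysis is a difference test, with no effect measure, interval criterion or reading of a non-significant result

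*SAP*

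**What the plan says.** **Aim.** The SAP's sample-size text on ambulatory function states: "We wish to demonstrate that the improvement in esophageal toxicity does not come at a price of reduced effect of the radiation". Protocol 3.4 carries the same text. The first SAP Purpose is "To investigate if esophagus-sparing radiotherapy can decrease patient reported dysphagia without compromising the" patient's walking. Protocol sections 2 and 3.1 state the same aim.

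**Label.** That SAP subsection is headed as a co-primary endpoint, but its text reads "As a prioritized secondary endpoint, we choose ambulatory function (preserved ability to walk) measured on a 4-point scale". The SAP Summary, Primary endpoints and Analysis A call walking co-primary, and the Analysis summary table calls it primary.

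**Test.** Analysis A.2, at 9 weeks: "Difference in scores between mobility dimension treatment arms will be compared using Wilcoxon rank-sum test". On the data used: "Primary analysis of EQ-5D-5L and EORTC-QLQ-C30 will only include completed questionnaires".

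**Decision.** The one stated consequence runs in one direction: "the power of the trial is enough to detect a deterioration according to the able, which would lead to rejection of the experimental treatment".

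**Intervals.** Under Statistical principles, 95% intervals are promised in general, with methods named as "calculated by the binominal distribution for rates and as per Kaplan-Meier method for time-to-event analyses". The Analysis section adds "We will report our data in accordance with the CONSORT 2010 guidelines". No effect measure or limit is named for the mobility comparison.

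**Missing data.** Deaths and missing forms are to be reported by arm. Sensitivity analyses are optional.

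**The concern.** A difference test asks whether the data contradict equality. Failing to contradict it is not evidence of equality, least of all in a trial where many patients may not provide the week-9 form. An aim of showing no loss needs an estimate, an interval and a statement of how large a loss has been ruled out. The SAP has none of these for walking.

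Protocol 6.4 allows the sparing plan to compromise PTV and CTV dose, so preserved walking is the counterweight to any dysphagia gain. Without a rule for the non-significant case, the reading would be chosen after the data are seen. The design also gives the wrong incentive: the fewer forms returned, the more likely a non-significant result becomes, even if walking is worse.

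**Working it through.** **Inputs.** From SAP Table 2, grades 1 to 4: conventional 22/44/26/8%, experimental 11/32/37/20%. Walking (grades 1–2) is 22 + 44 = 66% versus 11 + 32 = 43%, a loss of 23 points. The plan assumes 66 evaluable per arm of 100 randomized and a 0.05 significance level. Sidedness is not stated. Fifty evaluable per arm is added here as an assumption.

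**1. The plan's own figure.** Simulating Table 2 with 66 per arm and a tie-corrected Wilcoxon test gives 82.9% power at two-sided 0.05, against the stated 84%. One-sided 0.05 gives 89.9%, so two-sided is taken as the intended test. The stated power is not in dispute.

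**2. How often a real loss is missed.** Set experimental = conventional + f × (Table 2 experimental − conventional). Probability of a non-significant result:

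| True loss | Walking, points lost | 66 per arm | 50 per arm |
|---|---|---|---|
| Full Table 2 (f = 1) | 23 | 17% | 28% |
| Two thirds (f = 2/3) | 15.3 | 52% | 61.5% |
| Half (f = 1/2) | 11.5 | 70% | 76% |

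**3. What a non-significant result leaves open.** The effect measure that matches the Wilcoxon test is the Mann-Whitney probability: the chance that an experimental patient is worse than a conventional one, plus half the ties. For full Table 2:

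- Worse: 0.22 × 0.89 + 0.44 × 0.57 + 0.26 × 0.20 = 0.4986
- Ties: 0.22 × 0.11 + 0.44 × 0.32 + 0.26 × 0.37 + 0.08 × 0.20 = 0.2772
- Total: 0.4986 + 0.2772/2 = 0.637, where 0.5 means no difference

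Among simulated non-significant trials, the share whose 95% interval still reaches 0.637 is:

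| True state | 66 per arm | 50 per arm |
|---|---|---|
| No loss | 16% | 28% |
| Half loss | 58% | 70% |

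The non-significant label does not distinguish these cases. The interval does.

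**4. One concrete result.** Suppose 44/66 versus 33/66 are walking. The difference is 16.7 points. The pooled SE is √(0.5833 × 0.4167 × 2/66) = 0.0858, so z = 1.94 and a two-proportion test is non-significant. The unpooled SE is √(0.6667 × 0.3333/66 + 0.5 × 0.5/66) = 0.0846, so the upper limit is 16.7 + 1.96 × 8.46 = 33 points. That is beyond the 23-point loss that the SAP treats as grounds for rejection.

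**5. Whether an interval rule would be usable.** With no true difference, the Mann-Whitney interval excludes the full Table 2 loss about 82% of the time at 66 per arm and 71% at 50. On the proportion walking (66% in both arms, 66 per arm), SE = √(2 × 0.66 × 0.34/66) = 0.0825. The chance of excluding a loss M is Φ(M/SE − 1.96): 80% for 23 points and 44% for 15 points. The documents give no margin, so both values of M are illustrations.

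**The case against.** The strongest defence is that the SAP describes a harm check, not a non-inferiority claim. It names a loss, powers the trial to detect it and says what follows if it is seen. The wish to demonstrate is one sentence; the SAP Purpose speaks of investigating, and protocol 9.1 of examining.

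A reader might infer that the SAP treats non-significance as proof of preserved walking. It does not say so, and that reading should not be attributed to it. What stands is narrower: the stated aim has no route to a conclusion when the test is non-significant.

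A reader might also infer that dose compromise goes unguarded. It does not. Protocol 9.1 has re-irradiation rates in the two arms assessed continuously, and 8.3 and 9.1 let the trial management committee recommend cessation. Survival and pain response are compared as well. These are real safeguards, but none is a criterion for walking. For EQ-5D-5L, the Analysis summary names mixed models of the index and VAS, not the mobility item. Item O is a correlation of target coverage with ability to walk.

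The general promises of intervals and CONSORT reporting mean that an interval may well appear in the paper. No passage ties it to the conclusion.

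Finally, the simulations use the 4-point planning grade, not the 5-level EQ-5D-5L item. That limits the precision of the figures, not the logic.

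**Conclusion.** The point holds, and it should be settled before the walking results are read, because the planned analysis cannot answer half of the trial's own question. It can detect a loss of Table 2 size with about 83% power. A non-significant result cannot establish preserved walking: a half-size loss is missed about 70% of the time at 66 per arm, and 16% (no true loss) to 58% (half loss) of non-significant results remain compatible with the full Table 2 loss.

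These figures rest on the 4-point grade, a two-sided 0.05 test and the plan's 66 evaluable per arm. The figures for 50 per arm are an assumption. The documents give no week-9 return rate, so they do not support saying that fewer than 66 will be evaluable. The low compliance mentioned in the SAP is only indirect evidence, since protocol 3.6 defines compliance on daily forms in the first two weeks. The absence of a criterion does not depend on any of these inputs.

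**What to change.** **Main change, in SAP A.2 and protocol 3.4.** Report the between-arm Mann-Whitney probability for the week-9 mobility item with its 95% interval. Give the difference in the proportion choosing the lowest mobility level (unable to walk), with its interval, as a supporting figure. Add wording such as: *A non-significant Wilcoxon test alone is not evidence that walking is preserved; the conclusion will be based on the 95% CI and will state the largest loss it does not exclude.*

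**Optional margin.** If the sponsor fixes and justifies a margin before any mobility result by arm is seen, conclude preservation only if the interval excludes it. With no margin, make no formal claim of preservation and report what the interval excludes, for example whether it excludes the Table 2 loss.

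**Label.** Use one label for the endpoint throughout.

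**Secondary change.** Make one sensitivity analysis mandatory: rank death before week 9 below the lowest mobility level, and report the same effect measure with its 95% interval. Show it beside the completed-forms result and the counts of deaths and missing forms by arm.

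**Cost.** Wording and one extra analysis, with no new data or patients. The walking claim becomes more modest: even with no true difference, the interval would fail to exclude the full Table 2 loss about 18% of the time at 66 per arm and 29% at 50. The death-ranked analysis mixes death with mobility, so it should stay a sensitivity analysis.

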3.4 Ambulatory function as a co-primary endpoint

We wish to demonstrate that the improvement in esophageal toxicity does not come at a price of reduced effect of the radiation. As a prioritized secondary endpoint, we choose ambulatory function (preserved ability to walk) measured on a 4-point scale. We assume that the conventional arm follows the distribution of the SCORAD trial and test our ability to detect a difference from an assumed inferior experimental arm in terms of ambulatory function, see Table 1.⁷

If the underlying “true” distribution on ambulatory grades is as depicted in the table and we assume 66 patients per arm are evaluable, we find that 84% of simulated trials would lead to statistically significant differences detected with a Wilcoxon rank sum test for comparing the trial arms. In other words, the power of the trial is enough to detect a deterioration according to the able, which would lead to rejection of the experimental treatment.

	Conventional arm	Experimental arm
Grade 1: Ambulatory without the use of walking aids	22	11
Grade 2: Ambulatory with walking aids	44	32
Grade 3: Unable to walk	26	37
Grade 4: Absence or flicker of motor power in any muscle group	8	20

Table 1: Distribution of ambulatory function. The conventional arm follows the SCORAD trial (7).

The power of ESO-SPARE is enough to detect a difference in ambulatory function as seen in Table 1.

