The PRO-CTCAE® items and information herein were developed by the Division of Cancer Control and Population Sciences in the NATIONAL CANCER INSTITUTE at the NATIONAL INSTITUTES OF HEALTH, in Bethesda, Maryland, U.S.A. Use of the PRO-CTCAE® is subject to NCI's Terms of Use.

Health Questionnaire

English version for the UK

Under each heading, please tick the ONE box that best describes your health TODAY.

MOBILITY

I have no problems in walking about	
I have slight problems in walking about	
I have moderate problems in walking about	
I have severe problems in walking about	
I am unable to walk about	

SELF-CARE

I have no problems washing or dressing myself	
I have slight problems washing or dressing myself	
I have moderate problems washing or dressing myself	
I have severe problems washing or dressing myself	
I am unable to wash or dress myself	

USUAL ACTIVITIES (e.g. work, study, housework, family or leisure activities)

I have no problems doing my usual activities	
I have slight problems doing my usual activities	
I have moderate problems doing my usual activities	
I have severe problems doing my usual activities	
I am unable to do my usual activities	

PAIN / DISCOMFORT

[figure not shown]
I have no pain or discomfort	
I have slight pain or discomfort	
I have moderate pain or discomfort	
I have severe pain or discomfort	
I have extreme pain or discomfort	

ANXIETY / DEPRESSION

I am not anxious or depressed	
I am slightly anxious or depressed	
I am moderately anxious or depressed	
I am severely anxious or depressed	
I am extremely anxious or depressed	

- We would like to know how good or bad your health is TODAY.
- This scale is numbered from 0 to 100.
- 100 means the best health you can imagine.
0 means the worst health you can imagine.
- Please mark an X on the scale to indicate how your health is TODAY.

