Data are reported by the patient in a paper-edition trial diary, by electronic questionnaires or by telephone consultations. Survival data, re-irradiation, and hospitalization data are derived from patient's treatment records. After the results of an interim analysis revealing low compliance (1), weekly CTC registrations were implemented for all patients in the first 5 weeks after treatment start (from patient No. 107).

Table 1. Follow-up schedule in the ESO-SPARE trial

	Treatment start	Daily	Weekly	Weekly
		1-5 weeks	1-5 weeks	1-9 weeks
PRO-CTC-AE: Dysphagia, nausea, dyspepsia	X	X		
CTC-AE 5.0*	X		X	
EORTC-QLQ-C30 and EQ-5D-5L	X			X
Medication: Analgesics, corticosteroids, antiemetics	X			
Weight	X			X

*Starting from patient No. 107

Estimated Enrollment: 200 patients.

Allocation: Patients are randomized 1:1 to either esophagus-sparring treatment or standard treatment. Patients are stratified by center and fractionation. Randomization is performed in REDCap using random allocation with a block size of four and six.

Masking: Single-blind. Patients are blinded to randomization outcome.

Study Start Date: May 2021

Estimated Primary Completion Date: April 2024

Study Completion Date: The last patient will be included on April 30, 2024, or after the inclusion of 200 patients, whichever comes first.

Timing of final analysis

Following study closure, nine weeks of follow-up after radiotherapy start will be allowed for all patients, at which point data will be collected for primary end-point analysis. Analysis of data in respect to secondary endpoints and exploratory studies might be analyzed at any point of time, at the discretion of the study group.

Data

Data are captured in REDCap. Data will be kept in databases 10 years after the last patient is included.

[Sample size](#)

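### The 84% power for the ambulatory co-primary endpoint is calculated on a 4-grade scale, not on the 5-level EQ-5D-5L mobility item that will be tested; under a literal mapping it is about 79%

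*SAP*

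**What the plan says.** Protocol 2.2 and the SAP's list of primary endpoints define the ambulatory co-primary endpoint by EQ-5D-5L mobility. SAP Analysis A.2 fixes the time at nine weeks and the test as Wilcoxon rank-sum. It describes the instrument thus: "Each dimension has 5 levels depending on the severity of symptoms". In the questionnaire (Protocol, Appendix B) the mobility item has four levels for people who can walk, from no problems to severe problems, and one for those who cannot: "I am unable to walk about".

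The power section, nearly identical in Protocol 3.4 and the SAP, describes something else: "As a prioritized secondary endpoint, we choose ambulatory function (preserved ability to walk) measured on a 4-point scale". Its table has two walking grades (without and with aids) and two non-walking grades (unable to walk; little or no motor power). On that table the SAP says "we assume 66 patients per arm are evaluable, we find that 84% of simulated trials would lead to statistically significant differences", and both documents conclude that the trial's power is sufficient for the tabulated difference.

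No section links the four grades to the five EQ-5D levels or gives a planning distribution on the EQ-5D item.

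**The concern.** Power belongs to a test of a particular variable with a particular assumed distribution. Here the test is the same in both places, but the variable is not. The planning scale separates two degrees of non-walking that the mobility item cannot tell apart, and it groups walkers by use of aids, which the mobility item does not ask about.

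This matters because of how the result will be used. The section's stated aim is to show that lower oesophageal toxicity is not bought with a weaker radiation effect, and Protocol 6.4 accepts lower target dose in the experimental arm where needed. The comparison is a plain difference test without a margin. A non-significant result is therefore likely to be read as reassurance, and that reading is only as good as the power behind it.

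**Working it through.** **Inputs.** 66 evaluable per arm and the Wilcoxon test (Protocol 3.4; SAP, Sample size). 1:1 allocation (SAP, Trial design). Significance level from SAP, Statistical principles: "Level of significance: $p < 0.05$ with no adjustment for multiplicity". Sidedness is not stated, so two-sided is assumed. Grade percentages from the planning table: 22/44/26/8 conventional, 11/32/37/20 experimental.

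**Formula.** Let p and q be the conventional and experimental proportions, ordered from best to worst, and n = 66.

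- θ = P(experimental worse) + ½ P(tie) = Σ q_i (p_1 + … + p_(i−1) + ½ p_i)
- Null standard error: SE0 = √[ (1 − Σ m_i³)/12 × 2/n ], with m_i = (p_i + q_i)/2
- Standard error under the alternative: SE1 = √[(V_q + V_p)/n], where V_q and V_p are the variances of each arm's mid-rank scores relative to the other arm
- Power = Φ[ (θ − 0.5 − 1.96 × SE0) / SE1 ]

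**Step 1: reproduce the plan's figure (four grades).**

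- θ = 0.11×0.11 + 0.32×0.44 + 0.37×0.79 + 0.20×0.96 = 0.6372
- Σ m³ = 0.165³ + 0.38³ + 0.315³ + 0.14³ = 0.0934, so SE0 = 0.0478
- V_q = 0.0725 and V_p = 0.0643, so SE1 = √(0.1368/66) = 0.0455
- Power = Φ[(0.1372 − 0.0938)/0.0455] = Φ(0.954) = 83.0%

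Simulation with 200,000 trials gives 82.8%. The stated 84% is reproduced to within about a point. One-sided 0.05 would give 89.8%, so two-sided is the reading that fits.

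**Step 2: literal mapping.** Put grades 3 and 4 into the single non-walking level and keep walkers in two classes: 26 + 8 = 34 and 37 + 20 = 57, that is 22/44/34 against 11/32/57.

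- θ = 0.11×0.11 + 0.32×0.44 + 0.57×0.83 = 0.626
- Σ m³ = 0.165³ + 0.38³ + 0.455³ = 0.1536, so SE0 = 0.0462
- V_q = 0.0641 and V_p = 0.0667, so SE1 = √(0.1308/66) = 0.0445
- Power = Φ[(0.126 − 0.0906)/0.0445] = Φ(0.795) = 78.7%

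Simulations give 78.5% to 78.9%. The chance of missing the planned deterioration is 100 − 79 = 21%, against 100 − 84 = 16% as stated. Like for like the loss is 83 − 79 = 4 points. About 76 evaluable per arm would bring this version back to 84%.

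**Step 3: other mappings.** Each is an assumption, since the documents give none. All use 66 per arm.

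| Assumption | Power |
|---|---|
| Grades 3 and 4 in the non-walking level; each walking grade split evenly into two levels, same in both arms | about 77% |
| As above, but walkers spread over levels 1–4 by any common rule (200,000 random mappings) | median about 70%, lowest 59%, none above 78.7% |
| Table's cumulative odds ratios (2.28, 2.57, 2.88) also act smoothly between walking levels | 80–81% |
| Each walking grade split 50/50 in the conventional arm, 40/60 (better/worse) in the experimental arm | 82% |
| Same, with 30/70 in the experimental arm | 86% |
| Half of grade 3 patients tick severe problems rather than unable to walk; walkers keep two lower levels | 79% |
| All grade 3 patients do so | 83% |

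The odds ratios come from the table. At the first cut, for example, (0.22/0.78)/(0.11/0.89) = 2.28.

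**The case against.** The best defence is that the five-level item may lose little or nothing. It has four walking levels where the planning scale has two, and a treatment that moves patients between grades could also move walkers from slight to severe problems. The table gives only grade percentages and is silent on what happens within a grade. This stands, and it rules out several stronger conclusions that a reader might draw.

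- **That 79% is a ceiling and the miss rate at least 21%.** This needs every grade 3 and grade 4 patient to tick the non-walking level, and the EQ-5D answer to depend on grade alone, by the same rule in both arms. The documents state neither, and step 3 shows power above 79% when either is relaxed.
- **That the assumed rise in grade 4 from 8% to 20% disappears.** The merged category still moves from 34% to 57%, which includes those 12 points. Only the distinction between the two non-walking grades is lost, which is why the fall in power is modest.
- **That this test is the trial's only formal check on loss of effect.** The SAP also compares pain response, re-irradiation at the primary site and overall survival between arms, and Protocol 8.3 and 9.1 provide for review of re-irradiation. It is the only such check with co-primary status.
- **That the sponsor miscalculated.** The 84% is sound for its own table.

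It is also fair to say that the claim of sufficient power is tied to the tabulated difference. But that table is not on the scale of the endpoint, so the condition does not repair the claim.

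**Conclusion.** The concern holds as a mismatch between planning scale and endpoint. The documents give no power for the test they plan. Under the literal reading of the grade labels power is about 79% rather than 84%; of that gap about 4 points come from the change of scale and about 1 from the difference between the stated and reproduced figures. Under other plausible mappings it is roughly 70% to 83%, and a larger shift among walkers would take it higher. The direction is therefore likely but not certain, and the size depends on assumptions that the sponsor has not stated.

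All figures assume 66 evaluable patients per arm, two-sided 0.05 and the planning table's percentages. Whether 66 per arm will be evaluable at nine weeks is a separate question. The mismatch alters no test, estimate or analysis set. It bears on how much reassurance a non-significant ambulatory result can carry.

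**What to change.** In the SAP's sample-size section:

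1. Give an assumed distribution over the five EQ-5D-5L mobility levels at week 9 for each arm, and say how it was derived from the four-grade table.
2. Re-run the Wilcoxon simulation on that distribution, stating sidedness and the number evaluable.
3. Replace 84% by the result and its mapping assumptions, with a short sensitivity range. On present inputs this is about 79% under the literal mapping and roughly 70–83% under other plausible mappings. Do not present 79% as a maximum.
4. Word the statement that power is sufficient so that it applies only to the assumed EQ-5D distribution.

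The cost is one simulation and a paragraph of text; the design and the planned test stay as they are. The drawback for the sponsor is that the stated power will probably be slightly less favourable.
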